3.3.4 Removal of patients from therapy or assessments

3.3.4.1 Removal of individual patients

The treatment with nintedanib has to be permanently discontinued in the following circumstances:

- Liver function impairment (refer to [Section 10.1](#)):
 - ALT or AST \geq 8 fold ULN.
 - ALT or AST \geq 3 fold ULN for more than 2 weeks despite dose reduction.
 - ALT or AST \geq 3 fold ULN and total bilirubin $>$ 1.5 fold ULN.
 - ALT or AST \geq 3 fold ULN and INR $>$ 1.5.
 - ALT or AST \geq 3 fold ULN with the appearance of fatigue, nausea, vomiting, right upper abdominal quadrant pain or tenderness, fever, rash, and/or eosinophilia ($>$ 5%).
- Diarrhoea: reoccurrence of diarrhoea ($>$ 4 stools/day) for 8 or more consecutive days despite dose reduction and supportive care as described in [Section 4.2.1.1](#).
- Pregnancy (refer to [Section 5.3.7](#)).
- Planned usage of a specific investigational drug (refer to [Section 4.2.2.1](#)).
- Treatment interruption. Treatment interruption is acceptable in certain cases and for a defined period which are described in [Section 4.2.1](#).

Similar to the parent study, in the following cases withdrawal of study drug is highly recommended. Only in special circumstances, the investigator, upon thorough assessment of all available clinical data, and taking into consideration the potential risks associated with administration of nintedanib, may decide not to withdraw the patient, even though one or more of the below mentioned criteria are fulfilled. However, in such a case, continuation of study treatment should be discussed with the patient, and the decision documented in the source data.

Proprietary confidential information.

© 2017 Boehringer Ingelheim International GmbH or one or more of its affiliated companies. All rights reserved.

This document may not - in full or in part - be passed on, reproduced, published or otherwise used without prior written permission.

- Planned major surgery, including any major abdominal or intestinal surgery.
- Patients who require full-dose therapeutic anticoagulation (e.g. vitamin K antagonists, dabigatran, heparin, hirudin), or high-dose antiplatelet therapy.
- Major thrombo-embolic events e.g. stroke, deep vein thrombosis, pulmonary embolism, myocardial infarction.
- Increased risk of bleeding e.g. haemorrhagic CNS event, gross / frank haemoptysis or haematuria, active gastro-intestinal bleeding or ulcers.

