4.2.2 Restrictions

4.2.2.1 Restrictions regarding concomitant treatment

- Investigational therapy is not allowed during the entire study period and must not have been introduced in the interval between parent trial and enrolment into this extension trial.
- Nintedanib is an anti-fibrotic kinase inhibitor which has been shown to have anti-angiogenic properties. Inhibition of angiogenesis may increase susceptibility to bleeding. Therefore, concomitant anticoagulation, fibrinolysis or high-dose antiplatelet therapy is contra-indicated (refer to [Section 3.3.3](#) [4 weeks washout]). Patients who require fibrinolysis, full-dose therapeutic anticoagulation (e.g. vitamin K antagonists, dabigatran, heparin, hirudin), or high dose antiplatelet therapy are to be withdrawn. Prophylactic low dose heparin or heparin flush as needed for maintenance of an indwelling intravenous device (e.g. enoxaparin 4000 IU s.c. per day), as well as prophylactic use of antiplatelet therapy (e.g. acetyl salicylic acid up to 325 mg/d, or clopidogrel at 75 mg/d, or equivalent doses of other antiplatelet therapy) should be allowed.
- The concomitant administration of nintedanib with any drugs which are likely to increase gastrointestinal events such as diarrhoea, nausea, vomiting, is discouraged.
- Washout of bronchodilators must be observed before spirometry: 24 hours for long acting and 8 hours for short acting bronchodilators, if applicable.

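### SAP violation D1 omits the dose limit on antiplatelet therapy, and Protocol 3.3.4.1 and 4.2.2.1 disagree on whether patients needing full-dose anticoagulation or high-dose antiplatelet therapy must stop nintedanib

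*Protocol*

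**What the plan says.** Protocol 3.3.4.1 has two lists. The first gives circumstances in which nintedanib must be stopped permanently. The second opens by saying that "in the following cases withdrawal of study drug is highly recommended", and it includes "Patients who require full-dose therapeutic anticoagulation (e.g. vitamin K antagonists, dabigatran, heparin, hirudin), or high-dose antiplatelet therapy". For this second list the investigator, in special circumstances and after a thorough assessment, "may decide not to withdraw the patient, even though one or more of the below mentioned criteria are fulfilled". The condition is that "continuation of study treatment should be discussed with the patient, and the decision documented in the source data".

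Protocol 4.2.2.1 is stricter. Because of the bleeding risk, "concomitant anticoagulation, fibrinolysis or high-dose antiplatelet therapy is contra-indicated". It continues: "Patients who require fibrinolysis, full-dose therapeutic anticoagulation (e.g. vitamin K antagonists, dabigatran, heparin, hirudin), or high dose antiplatelet therapy are to be withdrawn". The same paragraph permits "prophylactic use of antiplatelet therapy (e.g. acetyl salicylic acid up to 325 mg/d, or clopidogrel at 75 mg/d", or an equivalent dose of another agent. Exclusion criterion 3a in Protocol 3.3.3 makes the same prophylactic exception at entry.

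Protocol 4.2.1.3 lets a patient with an acute exacerbation interrupt nintedanib for up to 8 weeks, and gives short-term full anticoagulation as an example of when this may be needed.

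Protocol 7.3 leaves the definition of important violations, including those for prohibited medications, to the SAP. In SAP Table 6.2: 1, D1 covers prohibited medication in the treatment period. Its four bullets are investigational therapy, full-dose anticoagulation, fibrinolysis and antiplatelet therapy. It is flagged as safety and identified by manual review of listings.

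**The concern.** There are two separate problems. First, D1 as worded takes in treatment that the protocol allows. Prophylactic aspirin or clopidogrel would be listed as a prohibited-medication safety violation.

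Second, a site with a patient who comes to need full-dose anticoagulation gets different instructions depending on the section it reads. One allows documented continuation and the other requires withdrawal. An investigator who uses the discretion in 3.3.4.1 correctly has still departed from 4.2.2.1, and appears under D1 with nothing to show that the decision was permitted.

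Bleeding is the stated reason for the restriction and is a dedicated adverse event topic in SAP Table 7.8.1:1. The rule also stays in force after the database lock for the final analysis. Under Protocol 6.2.5 the remaining patients are treated until a reason for discontinuation in 3.3.4 is met or they obtain nintedanib elsewhere, while under 5.3.3 the trial laboratory tests, which include INR and PTT, are no longer done.

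**Working it through.** The documents state no figure on this point, so the check compares the texts.

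**Step 1. What each place says.**

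| Place | Applies | High-dose qualifier on antiplatelets | Prophylactic doses given | Status |
|---|---|---|---|---|
| Protocol 3.3.3, criterion 3a | Entry only | Yes | Yes | Excluded |
| Protocol 3.3.4.1 | On treatment | Yes | No | Withdrawal recommended, discretion allowed |
| Protocol 4.2.2.1 | On treatment | Yes | Yes | Contra-indicated, withdrawal without exception |
| SAP D1 | On treatment, classification only | No | No | Safety violation |

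D1 does carry a qualifier on its anticoagulation bullet, which is limited to full dose. The missing qualifier two bullets later therefore reads as covering every dose.

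**Step 2. Apply the texts to four patients.**

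| Patient | 3.3.4.1 | 4.2.2.1 | D1 as written |
|---|---|---|---|
| A: clopidogrel 75 mg/d, stays on nintedanib | Not on the list | Allowed | Violation |
| B: needs full-dose anticoagulation, nintedanib withdrawn | Complies | Complies | No use while on treatment after withdrawal |
| C: needs full-dose anticoagulation, continued with documentation | Permitted | Contrary | Violation |
| D: short-term full anticoagulation in an acute exacerbation, nintedanib interrupted | Interruption accepted by reference to 4.2.1 | No exception stated | Outside D1 |

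Patient D falls outside D1 because SAP 6.1 ends the treatment period at an interruption and places the gap in a separate off-treatment period.

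**Step 3. Locate the defects.** Patient A shows a D1 definition that disagrees with the protocol, whichever way the withdrawal rule is settled. Patient C shows the conflict between the two protocol sections. It arises only when the discretion is used, since withdrawal (patient B) satisfies both. Patient D shows an exception that 4.2.2.1 should name but does not.

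**Step 4. Look for a rule of precedence.** 3.3.4.1 refers to 4.2.2.1 once, for planned use of an investigational drug, which is on its mandatory list. It does not refer to 4.2.2.1 for anticoagulation. 4.2.2.1 does not refer to 3.3.4.1 at all. Neither says which governs.

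**Step 5. Follow the effect into the analysis.** SAP 6.2 says that violations are only described and that no patient is excluded because of them. Analyses use the Treated Set, so the number of patients removed is 0. Neither document counts patients who need these therapies, take prophylactic antiplatelets or are continued under the discretion, so the number affected cannot be estimated.

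**The case against.** The strongest reply on D1 is that its row is headed as prohibited medication, and prophylactic antiplatelet use is not prohibited. SAP section 3 assumes the reader knows the protocol, and D1 is reviewed manually, so a reviewer can apply the dose limit. This lowers the practical risk. It does not correct the definition: the bullets state what is prohibited, and nothing in the SAP tells the reviewer to narrow this one.

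On the protocol, the sections can be read together, with 4.2.2.1 as the default and 3.3.4.1 as a narrow exception. The flow chart and several sections send discontinuation decisions to 3.3.4, and 3.3.4.1 says that its discretion follows the parent study, so it is probably deliberate. This is a reasonable reading, but the reader has to supply it, because 4.2.2.1 is unqualified.

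It is also fair to say that listing a documented continuation under D1 is not wrong in itself. SAP 6.2 defines safety violations as those that may affect patients' safety or rights, and nintedanib taken with full-dose anticoagulation fits that. Removing these patients from the listing would hide an exposure that a safety reader wants to see. This point stands and shapes the fix.

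A reader might infer that mandatory withdrawal is the right answer because more places prohibit these therapies than allow discretion. The documents do not support that. Criterion 3a applies only at entry and D1 is an analysis classification, so the protocol's on-treatment rules stand one against one. Mandatory withdrawal would also largely empty the discretion that 3.3.4.1 keeps for major thrombo-embolic events, for which anticoagulation is a common treatment.

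Two other wording points are tempting but add little. The "4 weeks washout" pointer in 4.2.2.1 leads to 3.3.3, which contains no washout, but it concerns entry. Entry had to fall within 12 weeks of parent Visit 9, and the parent reports date from April 2014, so in a March 2017 protocol it is clerical. Fibrinolysis is missing from the discretionary list in 3.3.4.1, but that is not a conflict, because 4.2.2.1 covers it alone.

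**Conclusion.** The point holds in two parts. D1 is wrong as written, because it lists permitted prophylactic antiplatelet use as a safety violation. Protocol 3.3.4.1 and 4.2.2.1 give incompatible instructions for a patient continued on full-dose anticoagulation or high-dose antiplatelet therapy, and no precedence is stated.

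The size is modest: bleeding-risk conduct at sites, and the accuracy of a descriptive listing. The number of patients is unknown and may be zero. A reader might infer that the primary adverse event summary is affected. It is not, since violations exclude no one and do not enter the calculation of incidence. The conclusion rests on the current wording alone. It does not assume that D1 was applied literally or that any patient was continued under the discretion.

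**What to change.** **SAP.** In D1, replace the antiplatelet bullet with *High-dose antiplatelet therapy (above the prophylactic doses allowed in CTP 4.2.2.1)*. This is one line and needs no protocol change.

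**Protocol.** Have the sponsor's clinical team choose one status for these patients and state it in both 3.3.4.1 and 4.2.2.1 with a cross-reference.

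- *If discretion is kept:* 4.2.2.1 should read *are to be withdrawn, except as provided in 3.3.4.1 or during an interruption under 4.2.1.3*. Documented continuations should stay in the violation listing, marked as permitted under 3.3.4.1.
- *If withdrawal becomes mandatory:* keep the 4.2.1.3 interruption as an explicit exception. SAP violation C7 lists patients not permanently discontinued despite meeting 3.3.4.1 criteria, so the exception prevents a patient who interrupts and restarts from being listed there. Align the thrombo-embolic event bullet as well, so that the two do not contradict each other.

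**Cost.** A few lines of text, with no new procedures or assessments. The protocol change needs ethics committee and authority approval under Protocol 8.1. Choosing mandatory withdrawal would also have a clinical cost: any patient now continued under the discretion would have to stop.

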3.3.4.2 Discontinuation of the trial by the sponsor

Boehringer Ingelheim reserves the right to discontinue the trial overall or at a particular trial site at any time for the following reasons:

1. Emergence of any efficacy/safety information that could significantly affect continuation of the trial,
2. Marketing authorization, availability for compassionate use or early access program offered by the sponsor (depending on local laws),
3. Violation of GCP, the CTP, or the contract by a trial site or investigator, disturbing the appropriate conduct of the trial.

Proprietary confidential information.

© 2017 Boehringer Ingelheim International GmbH or one or more of its affiliated companies. All rights reserved.

This document may not - in full or in part - be passed on, reproduced, published or otherwise used without prior written permission.

4. TREATMENTS

4.1 TREATMENTS TO BE ADMINISTERED

Nintedanib will be supplied by Boehringer Ingelheim Pharma GmbH & Co. KG.

4.1.1 Identity of BI investigational product and comparator product

All patients will be treated with nintedanib in this trial; there is no active comparator or placebo.

Substance:	nintedanib
Pharmaceutical form:	Soft gelatin capsule
Source:	BI Pharma GmbH & Co. KG
Unit strengths:	150 mg , 100 mg
Posology:	Twice daily (bid)
Route of administration:	Oral (swallowed)

4.1.2 Method of assigning patients to treatment groups

In the parent blind phase III trials (1199.32 and 1199.34) patients are assigned either active drug (nintedanib 150 mg bid) or placebo. In case patients experience adverse events related to drug tolerability, a dose reduction to 100 mg bid is allowed (both in active or placebo group).

At the end of treatment (Visit 9) in the parent trials, patients will be taking either 150 mg bid blinded study medication (active drug or placebo) or 100 mg bid blinded study medication (active drug or placebo) if their dose was permanently reduced during the trial.

Patients taking 150 mg bid blinded study medication (active drug or placebo) in the parent trial will be treated with nintedanib 150 mg bid in the current extension trial.

Patients who had the dose reduced to 100 mg bid (active drug or placebo) in the parent trial will be allowed to be treated with nintedanib 100 mg bid or 150 mg bid. This will ensure that patients who were on reduced dose placebo in the parent trial will have a chance to get the full dose in the extension trial.

The daily dose of nintedanib will be decided at Visit 2 based on discussion between the patient and the investigator.

Proprietary confidential information.

© 2017 Boehringer Ingelheim International GmbH or one or more of its affiliated companies. All rights reserved.

This document may not - in full or in part - be passed on, reproduced, published or otherwise used without prior written permission.

An Interactive Voice Response System (IVRS) will be used to assign medication numbers to eligible patients. Distribution of nintedanib to sites will be triggered by IVRS/IWRS.

Details on the IVRS/IWRS system are provided in the ISF.

After conclusion and unblinding of the parent trials, patients who received 100 mg bid (active drug or placebo) will also be allowed to increase their nintedanib dose to 150 mg bid, if this was not already performed at the beginning of the extension trial and if it is medically justified. In this situation, dose increase will need to be assigned through IVRS/IWRS during an additional visit (refer to [Section 6.2.4](#)).

4.1.3 Selection of doses in the trial

Based on the phase II safety and dose-finding trial 1199.30, a dose of 150 mg bid was selected for confirmatory phase III trials (1199.32/.34) ([U07-1248](#)). With 150 mg bid, the limit of tolerability in IPF patients is considered to be reached. Lower doses may not ensure full efficacy benefit. However, in case of lack of tolerability, the dose may be reduced temporarily or permanently to 100 mg bid.

4.1.4 Drug assignment and administration of doses for each patient

At Visit 2 patients who meet all eligibility criteria will be assigned trial drug: nintedanib either 150 mg or 100 mg bid (refer to [Section 4.1.2](#)).

Boxes covering 4 weeks + 1 week reserve treatment will be dispensed to the patient:

- 1 box at day 1 (Visit 2);
- 2 boxes at Visit 4;
- 3 boxes at Visits 6, 7 and 8;
- 4 boxes at Visit 9 and following visits.

Please refer to the [Flow Chart](#) for dispensing schedule. The investigational product should only be dispensed to participating patients according to the protocol by authorised personnel as documented in the form "Trial Staff List".

Study drug will be administered orally on a twice daily basis (bid). The patients should swallow the study medication unchewed together with a glass of water (~250 mL), and should observe a dose interval of 12 hours. Study drug should be taken at the same time every day (between 06:00 and 11:00 in the morning, and between 18:00 and 23:00 in the evening). Because nintedanib may cause stomach discomfort, it is recommended to take the drug after food consumption.

Proprietary confidential information.

© 2017 Boehringer Ingelheim International GmbH or one or more of its affiliated companies. All rights reserved.

This document may not - in full or in part - be passed on, reproduced, published or otherwise used without prior written permission.

If a patient forgets to take one or several doses of nintedanib he/she should take the following dose according to the protocol: no catch up of missed doses is permitted.

Patients on the 150 mg bid dose may have their dose permanently or temporarily reduced to 100 mg bid during the course of the extension trial for tolerability reasons, i.e. to manage adverse events (refer to [Section 4.2.1](#)). Dose reduction/re-escalation will need to be assigned through IVRS/IWRS during an additional visit (refer to [Section 6.2.4](#)).

4.1.5 Blinding and procedures for unblinding

4.1.5.1 Blinding

This is an open-label trial.

The previous treatment (active drug or placebo) in the blinded parent trials will remain unknown until the database lock of the parent studies.

4.1.5.2 Procedures for emergency unblinding

Not applicable.

4.1.6 Packaging, labelling and re-supply

Primary study material will consist of capsules containing nintedanib 150 mg or 100 mg. The colour of capsules between the two doses is slightly different.

All study medication will be packaged in one-week blister cards. Blister cards will be labelled with a unique identifier for drug accountability and will be labelled according to the regulatory requirements of the participating countries. Blisters will be packaged in one month boxes.

For details of packaging and the description of the label, refer to the ISF.

Re-supplies of study medication are planned due to the long duration of the study. The medication for re-supply will be packaged in an identical manner as the medication for initial supply.

4.1.7 Storage conditions

Nintedanib soft gelatin capsules will be stored in their original packaging under the recommended storage conditions, i.e. at room temperature at the study site. Detailed storage conditions are described on the study medication labels. The investigational product must be stored securely, e.g. in a locked cupboard or at a pharmacy.

Proprietary confidential information.

© 2017 Boehringer Ingelheim International GmbH or one or more of its affiliated companies. All rights reserved.

This document may not - in full or in part - be passed on, reproduced, published or otherwise used without prior written permission.

A temperature log must be maintained to make certain that the drug supplies are stored at the correct temperature.

If the storage conditions are found to be outside the specified range, immediately contact the sponsor as provided in the instructions for dispensing and storage in the ISF.

4.1.8 Drug accountability

Drug supplies, which will be provided by a CRO appointed by the sponsor, must be kept in a secure, limited access storage area under the storage conditions defined by the sponsor.

The investigator and/or pharmacist and/or investigational drug storage manager will receive the investigational drugs delivered by the sponsor when the following requirements are fulfilled:

- approval of the study protocol by the IRB / ethics committee,
- availability of a signed and dated clinical trial contract between the sponsor and the Principal Investigator / Head of Trial Centre,
- approval/notification of the regulatory authority, e.g. competent authority,
- availability of the curriculum vitae of the principal investigator,
- availability of a signed and dated clinical trial protocol or immediately imminent signing of the clinical trial protocol,
- for countries where it is required, availability of the proof of a medical licence for the principal investigator,
- for US, availability of the Form 1572.

The investigator and/or pharmacist and/or investigational drug storage manager must maintain records of the product's delivery to the trial site, the inventory at the site, the use by each patient, and the return to the sponsor or alternative disposition of unused product.

These records will include dates, quantities, batch/serial numbers, expiry ('use by') dates, and the unique code numbers assigned to the investigational product and trial patients. The investigator / pharmacist / investigational drug storage manager will maintain records that document adequately that the patients were provided the doses specified by the CTP and reconcile all investigational product received from the sponsor. At the time of return to the sponsor and/or appointed CRO, the investigator / pharmacist / investigational drug storage manager must verify that all unused or partially used drug supplies have been returned by the clinical trial patient and that no remaining supplies are in the investigator's possession.

Proprietary confidential information.

© 2017 Boehringer Ingelheim International GmbH or one or more of its affiliated companies. All rights reserved.

This document may not - in full or in part - be passed on, reproduced, published or otherwise used without prior written permission.

